8.2 In the Weeks Leading to Surgery (Outpatient)

During the time before the surgery, patients randomized to Group 1 will complete a daily PEP intervention as instructed by the physical therapist and record their activity on the tracking diary/calendar. The window before surgery may increase or decrease dependent on whether the patient is clinically and physically ready for surgery, as well as current surgical policies.

Weekly telephone calls or TeleHealth interactions (including video chat) between the patient and the study team will take place to answer questions, review exercise tracking/diary, and optimize patient engagement. Ongoing monitoring of attitudes and barriers to exercise will occur and strategies for encouraging uptake of the exercise intervention will be individually tailored. If needed, adjustments to the mode/dose of the exercise regimen will be made at the discretion of the physical therapist. These weekly phone calls may either be delayed or unsuccessful dependent on the participant's schedule, availability and whether or not they answer. However, study staff will make an effort to reach the participant if the participant continues to not answer or return the phone calls. In instances where a participant has felt burdened by these phone calls, research staff may perform the calls less frequently for these participants to maintain patient retention. Study staff may utilize text messaging and/or email in order to remind participants of future appointments/calls or to coordinate a day and time to reach the participant by phone. Study staff may also text and/or email the participants to send reminders, scheduling study procedures, etc..

8.3 Pre-Anesthesia Visit

- Correlative blood samples collection. Additional blood samples may be drawn before, during, or after this visit if needed. A blood questionnaire may be completed during the process of the blood draw, either before or after, to assist the study team with evaluation of the sample quality. Study staff may call the participant to ask questions from the blood questionnaire. If a participant declines the blood draw, the blood questionnaire will not be completed. Blood will not be collected if the Biospecimen and Molecular Pathology Shared Resource at the Huntsman Cancer Institute is closed at the time of collection.

8.4 Inpatient Stay

The inpatient stay post-surgery is expected to last from 5 to 10 days and may include assessments by the study physical therapist or inpatient physical therapists for all patients. The frequency of the assessments will follow standard of care guidelines and is dependent on the patient's condition.

8.5 Hospital Discharge Visit

This visit is directly aligned with the patient's clinic visits and is contingent on clinic and patient availability. The visit may occur 1 to 8 weeks from the date the patient was discharged from the hospital (discharge date) depending on the health of the patient and surgical policies. This window may increase if patient and surgical policies require it. The following procedures will be completed at the discharge visit. All procedures listed below can, as is practical and applicable, also be performed by the study team and participants via telephone, text, email, snail mail, and/or MyChart:

- Assessment by physical therapist including:
 - AM-PAC mobility score (outpatient form). Staff may perform the AM-PAC with the participant remotely if the form cannot be given in clinic.
 - Education on acute and sub-acute post-operative mobility limitations.
 - 6 Minute Walk test (6MWT) and Short Physical Performance Battery (SPPB). Efforts will be made to ensure consistent 6MW and SPPB testing conditions throughout data collection for each participant, but some modifications may be necessary during the COVID19 pandemic. Attempts will be made to complete both the 6MW and SPPB, but will not be completed situations where it is not safe for the participant per the treating physician or study physical therapist's discretion. Participants may have their results if they request them. Staff will attempt to complete the body measurements in clinic; however, the participant may also perform the measurements themselves at home. A measuring tape with the form to document the measurements may be mailed, emailed or provided to the participant directly. The participant may then perform the measurements themselves then return the form to staff via a prepaid envelope, email or via MyChart.
- Follow-up questionnaires and PROMIS (see section 7 for details). Staff will attempt to have PROMIS completed in clinic, but may mail or administer it via phone. The follow-up questionnaires may be mailed before the visit or given to participant at the

visit. Participants then may take the questionnaires home to be completed and returned the following weeks after the visit. Participants may also complete the questionnaire via phone with study staff after being seen in clinic if they wish. It is also an option for staff to email or send the questionnaire through the participant's electronic medical record (MyChart). The questionnaires and PROMIS may be administered remotely. The discharge questionnaire may be completed on the date of the visit up to the 2 month visit. It will not be considered a deviation if the questionnaire is not received as long as three attempts to remind the participant have been made.

- Distribution of tracking diary/calendar (2 month follow up only). The tracking diary/calendar results may be given to participants who request it. The diary may also be sent via email, mail, or the participant's electronic medical record (MyChart), if needed. It will not be a deviation if a participant does not return their diary as long as staff attempts to remind the participant to return it or if the participant declines to do it. The activity tracker may be mailed to the participant if staff is unable to administer in clinic.

Patients randomized to Group 1 will also receive the following:

- Review of home exercises and, if needed, adjustments to the mode/dose of the exercise regimen. This may be done in person, via phone, email, or remotely. The exercises may be mailed or sent via email or MyChart.

Staff may forego any of the above procedures if clinic policy does not allow (e.g. illness, virus outbreak, etc.).

If patients request to receive study materials and measurement results, the following may be given, mailed, emailed, or sent via MyChart:

Copy of exercise diary, 6MW, and their body measurements.

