5.2 Group 1-Intervention Group

The PEP intervention involves a combination of home-based exercise as well as in-patient exercise. The exercise modes will include basic transfer and calisthenics mobility, aerobic, and resistance exercises and will be performed in various postures (supine, sitting, standing, and walking) with variable challenges (level walking, bending, inclines, steps, and squatting).

For patients randomized to Group 1, the PEP intervention will be personalized, implemented, and modified (based on the patients AM-PAC mobility stage) by a licensed physical therapist in face-to-face, virtual, or phone meetings (~30-40 minutes). An exercise education manual, specifically developed for this study, will be used by the physical therapist to educate the patients on all aspects of starting and maintaining the exercise intervention.

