- Verification of the patient's eligibility for the study. The enrolling physician may sign the eligibility criteria via email, if necessary, however staff will try to receive their signature in person.
- Randomization. This may be completed remotely.
- Baseline assessments by study staff including:
 - Body measurements (height, weight, waist and hips measurements). Staff will attempt to complete the body measurements in clinic, however the participant

may perform the measurements themselves at home. A measuring tape with the form to document the measurements may be mailed, emailed, via MyChart or provided to the participant directly. The participant may then perform the measurements themselves then return the form to staff via a prepaid envelope, email or via MyChart.

- Medical history, medication use. (reviewed and assessed by clinic staff)
- AM-PAC mobility score (via the AM-PAC outpatient form). Staff may perform the AM-PAC with the participant via phone (remotely), if the form cannot be given in clinic.
- 6 Minute Walk Test (6MW) and Short Physical Performance Battery (SPPB). Efforts will be made to ensure consistent 6MW and SPPB testing conditions throughout data collection for each participant, but some modifications may be necessary during the COVID19 pandemic. These results may be mailed, emailed, sent via MyChart or recorded verbally via the video platform.
- Baseline questionnaires and PROMIS (all patients – details in Section 7). The PROMIS may be completed up to 1 week before and 3 weeks after the presurgery clinic visit. Staff will attempt to have PROMIS completed in clinic, but may mail, email, send through MyChart or perform it via phone either on site or remotely. The follow-up questionnaires may be mailed before or after the visit or given to participant at the visit. Participants then may take the questionnaires home to be completed and returned the following weeks after the visit. Participants may also complete the questionnaire via phone with study staff (either on site or remotely) after being seen in clinic if they wish. The questionnaires may also be sent via email, mail, or the participant's electronic medical record (MyChart). Staff will remind participants at least once to complete and return the questionnaire. It will not be considered a deviation if the questionnaire is not received as long as an attempt to remind the participant has been made.

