- 6 Minute Walk test (6MW) and Short Physical Performance Battery (SPPB). Efforts will be made to ensure consistent 6MW and SPPB testing conditions throughout data collection for each participant, but some modifications may be necessary during the COVID19 pandemic. Attempts will be made to complete both the 6MW and SPPB, but will not be completed situations where it is not safe for the participant per the treating physician or study physical therapist's discretion. These results may be mailed, emailed, sent via MyChart or recorded verbally via the video platform. Follow-up questionnaires and PROMIS. The PROMIS may be completed up to 3 weeks before or 3 weeks after each follow-up clinic visit. The follow-up questionnaires may be mailed before the visit or given to participant at the visit. Participants then may take the questionnaires home to be completed and returned the following weeks after the visit. Participants may also complete the questionnaire via phone with study staff after being seen in clinic if they wish. It is also an option for staff to email or send the questionnaire through the participant's electronic medical record (MyChart). The PROMIS and questionnaires may be administered remotely, if needed. It will not be considered a deviation if the follow-up questionnaires are not received as long as at least three attempts to remind the participant have been made.
- 7 Day Physical Activity Recall (performed via phone, remotely or on-site, or during the visit). This may be completed up to 2 weeks before the visit. It will not be considered a deviation if the 7-Day Physical Activity Recall is not received as long as three attempts are made.
- Body measurements (baseline, discharge, 2 month and 6 month follow up). Staff will attempt to complete the body measurements in clinic under appropriate safety precautions, however the participant may perform the measurements themselves at home. A measuring tape with the form to document the measurements may be mailed, emailed or provided to the participant directly. The participant may then perform the measurements themselves then return the form to staff via a prepaid envelope, email or via MyChart.

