10 STATISTICAL CONSIDERATIONS

10.1 Randomization

Randomization will have a uniform 1:1 allocation ratio with block sizes of 8. The random allocation sequence will be stratified by the mobility staging (high vs. low) provided by the pre-treatment AM-PAC stage and whether it is a primary or secondary lung cancer diagnosis, based on primary data (as described in section 2.4), the AMPAC stage is sufficient to assess physical function.

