10.3 Primary Endpoint Analysis

Analyses will include all patients that are evaluable for our primary endpoint (expected at least $n=150$). The primary outcome will be the group effect for an analysis of covariance model with 6MW test at 2 months post-surgery as outcome and pretreatment 6MW test as covariate, tested at the nominal two-sided 0.05 significance level. A sensitivity analysis will be performed with additional adjustment variables (listed as covariates in Section 10.1). Missing data will be handled using multivariate imputation by chained equations⁸⁸ as implemented in the R package “mice”.

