11 REGISTRATION GUIDELINES

Patients must meet all of the eligibility requirements listed in Section 5 prior to registration.

Patients must not have any study procedures or begin protocol treatment prior to registration.

Randomization to the Intervention or Control Arm will be done at the time of enrollment by the enrolling coordinator using OnCore (the Clinical Trials Office’s electronic clinical research management system).

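### The order of allocation and baseline testing is contradictory, so the baseline walk can follow disclosure of the arm, and no masking of the 6MW/SPPB assessor is described

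*Combined protocol and SAP*

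**What the plan says.** **Order at baseline.** Section 8.1 lists consent, eligibility, randomisation (which may be done remotely) and then "Baseline assessments by study staff including" the AM-PAC, 6MW and SPPB. Section 11 states that "Patients must not have any study procedures or begin protocol treatment prior to registration" and has the enrolling coordinator randomise at enrolment. Section 10.1 has the allocation sequence "stratified by the mobility staging (high vs. low) provided by the pre-treatment AM-PAC stage".

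**Primary analysis.** Section 10.3: "The primary outcome will be the group effect for an analysis of covariance model with 6MW test at 2 months post-surgery as outcome", with the pretreatment 6MW as its covariate.

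**Who delivers and who tests.** Under Section 5.2, PEP is "personalized, implemented, and modified (based on the patients AM-PAC mobility stage) by a licensed physical therapist". At discharge (Section 8.5), the 6MW and SPPB sit under "Assessment by physical therapist including". At 2 and 6 months (Section 8.7), the therapist's item names only the AM-PAC. The 6MW and SPPB form a separate item with no tester named. Section 8.7 also places diary review and any change to the exercise regimen for Group 1 at these visits.

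**Omitting the test.** Sections 8.5 and 8.7 say that both tests will be attempted, but that they "will not be completed situations where it is not safe for the participant per the treating physician or study physical therapist's discretion".

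**Masking.** None is described in the text supplied. The safeguard offered is consistent testing conditions for each participant.

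**The concern.** Six-minute distance responds to encouragement, pacing and the walker's own effort. Patients cannot be masked to an exercise programme. What the plan can control is when the baseline walk is done and what the tester knows.

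If the baseline walk follows allocation, the covariate is no longer certain to be free of the treatment. An arm-related shift in it passes into the adjusted difference. At 2 months, arm-related encouragement adds directly to the estimated effect. If walks are left out for different reasons in the two arms, the tested patients also stop being comparable.

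**Working it through.** **Step 1: can the three ordering provisions all be followed?**

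| Section | What it implies |
|---|---|
| 8.1 | Randomisation is listed before AM-PAC, 6MW and SPPB |
| 11 | No study procedures before registration; randomisation at enrolment |
| 10.1 | AM-PAC stage must be known before allocation |

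Not as listed. AM-PAC cannot both follow randomisation and stratify it. Section 8.1 also allows a route that satisfies 10.1 and still puts the walk last. Consent, AM-PAC and randomisation may all be done remotely, and remote procedures may be completed before the in-person appointment. A patient could give AM-PAC answers by phone, be allocated, and walk later. Nothing requires the walk to come before allocation.

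**Step 2: the plan's own figures.**

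- Inputs (Sections 10.2 and 10.3): difference 39.95 m, SD 100 m, correlation 0.5, two-sided 0.05, 200 randomised, 25% dropout.
- Evaluable: 200 × 0.75 = 150, or 75 per arm, as stated.
- ANCOVA residual SD = 100 × √(1 − 0.5²) = 86.6 m.
- The plan prints no power for the primary test. Assuming 80%, the requirement is 74 per arm, 148 in total; 148 / 0.75 = 197.3, so 198 against the stated 200. Power with 75 per arm is about 80% (0.806 by formula, 0.798 by simulation).

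The sample size reproduces, and nothing here changes it.

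**Step 3: standard error.** SE = 86.6 × √(2/75) = 14.14 m. A difference of about 1.96 × 14.14 = 27.7 m is significant.

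**Step 4: spurious difference at 2 months, no true effect.** For a bias b, the rejection rate is 1 − Φ(1.96 − b/SE) + Φ(−1.96 − b/SE).

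| b (assumed) | b/SE | Rejection rate |
|---|---|---|
| 0 m | 0 | 5.0% |
| 5 m | 0.354 | 6.4% |
| 10 m | 0.707 | 10.9% |
| 20 m | 1.414 | 29.3% |

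**Step 5: shift at baseline.** The within-arm slope is 0.5 (equal SDs, correlation 0.5), so a baseline shift c towards Group 1 changes the estimate by −0.5c.

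- 10 m towards Group 1 at both visits: net 10 − 5 = 5 m, so 6.4% and not 10.9%.
- 10 m towards Group 1 at baseline only: −5 m, a bias against PEP.
- 10 m towards Group 2 at baseline only: +5 m, 6.4%.

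**Step 6: selective omission.** This was simulated with no true effect, 100 per arm and 25 untested per arm. If the 5 lowest walkers in the PEP arm are among the untested and all other omissions are random, the mean spurious gain is 8 m and the rejection rate about 10%. This is an extreme pattern analysed on tested patients only, without the planned multiple imputation. It shows why the reasons for omission need recording; it does not predict what will happen.

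**The case against.** A reader might infer something stronger: that staff know the arm at every test, that the therapist who delivers PEP runs the primary walk, and that this therapist is free to skip it. The documents do not support that.

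- Knowledge of arm at every test is inferred from silence on masking; it is not stated. The list in 8.1 is not a strict timeline: its last item, the 7-day recall, may be done up to two weeks before the visit. What is shown is an unresolved order, not that allocation always comes first.
- Therapist testing is explicit only at discharge, a visit the primary ANCOVA does not use. Section 8.7 names no tester, and the schedule in Section 6 keeps the 6MW and SPPB rows apart from the therapist-assessment row, which is marked as due for PEP patients only.
- Omission is limited to cases where the walk is not safe, and the decision lies "per the treating physician or study physical therapist's discretion" (Section 8.7, as in 8.5), so the therapist is one of two possible deciders.
- Missing values are to be multiply imputed. That would not in general remove bias from omissions tied to unrecorded poor function, and Section 10.3 plans no sensitivity analysis for this, but it bears on the size of the harm.
- The bias sizes have no source in the documents, and biases acting at both visits partly cancel.
- Section 9.1 refers to operating procedures for the 6MW that are not reproduced, so a fixed script may already exist.

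All of this stands and limits the point. It does not remove the contradiction between 8.1, 10.1 and 11, or supply any masking provision. An unnamed tester at the primary visit is itself a gap, and more so because Group 1 diary review and exercise adjustment fall at that visit.

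**Conclusion.** The point holds in limited form. The order of allocation and baseline testing is contradictory, and as written the sole covariate of the primary analysis can be measured after the arm is known. No assessor masking is described for an effort-dependent primary endpoint, and the 2-month tester is unnamed.

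With SE 14.14 m (SD 100 m, correlation 0.5, 75 per arm), an assumed arm-related difference of 5 to 20 m at 2 months moves the false-positive rate from 5% to between 6.4% and 29.3%. Half of any same-direction shift at baseline is subtracted from that difference. These figures show sensitivity to assumed biases; they do not show that a bias will occur. The absence of masking is established only for the text supplied.

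**What to change.** 1. Reconcile Sections 8.1, 10.1 and 11 so that, after consent and registration, the AM-PAC, 6MW and SPPB are completed before the OnCore allocation is opened. Section 11 would need to separate registration from randomisation. The cost is wording and visit order; where consent is remote, allocation waits for the baseline walk.
2. In Sections 8.5 and 8.7, run the 6MW and SPPB before any diary review or exercise adjustment, with one fixed encouragement script in both arms. Where existing staffing allows, name a tester who neither prescribes PEP nor makes the weekly Group 1 calls. Sequence and script cost little. A separate tester costs scheduling and may not be possible without extra staff: the study team makes those calls, and in the pilot (Section 2.7) a physical therapist did both the testing and the prescribing. Some unmasking by patients will remain.
3. Leave the safety decision on omitting a walk as written. Record who decided and why, and report omissions by arm. The cost is a short addition to the case report form and one table.

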8.6 During the Follow-Up (Outpatient)

For patients randomized to Group 1, weekly telephone calls or TeleHealth interactions between the participant and the study team will continue as described in section 8.2.

8.7 Follow-Up Clinic Visits (2 and 6 Months Post-Surgery).

These visits are directly aligned with the patient's clinic visits and is contingent on clinic and patient availability. During times of unforeseen external impact, the 2 month visit may occur up to 4 months post-discharge and the 6 month visit may be completed up to one year post-discharge depending on the health of the patient and surgical policies. This window may increase if patient and surgical policies require it. The 6 month questionnaire may be completed on the date of the visit up to one year after the visit. The following procedures will be completed at the follow-up visits scheduled approximately 2 and 6 months after surgery:

- Assessment by physical therapist including AM-PAC mobility score (outpatient form). Staff may administer the AM-PAC with the participant remotely if the form cannot be given in clinic.
- 6 Minute Walk test (6MW) and Short Physical Performance Battery (SPPB). Efforts will be made to ensure consistent 6MW and SPPB testing conditions throughout data collection for each participant, but some modifications may be necessary during the COVID19 pandemic. Attempts will be made to complete both the 6MW and SPPB, but will not be completed situations where it is not safe for the participant per the treating physician or study physical therapist's discretion. These results may be mailed, emailed, sent via MyChart or recorded verbally via the video platform. Follow-up questionnaires and PROMIS. The PROMIS may be completed up to 3 weeks before or 3 weeks after each follow-up clinic visit. The follow-up questionnaires may be mailed before the visit or given to participant at the visit. Participants then may take the questionnaires home to be completed and returned the following weeks after the visit. Participants may also complete the questionnaire via phone with study staff after being seen in clinic if they wish. It is also an option for staff to email or send the questionnaire through the participant's electronic medical record (MyChart). The PROMIS and questionnaires may be administered remotely, if needed. It will not be considered a deviation if the follow-up questionnaires are not received as long as at least three attempts to remind the participant have been made.
- 7 Day Physical Activity Recall (performed via phone, remotely or on-site, or during the visit). This may be completed up to 2 weeks before the visit. It will not be considered a deviation if the 7-Day Physical Activity Recall is not received as long as three attempts are made.
- Body measurements (baseline, discharge, 2 month and 6 month follow up). Staff will attempt to complete the body measurements in clinic under appropriate safety precautions, however the participant may perform the measurements themselves at home. A measuring tape with the form to document the measurements may be mailed, emailed or provided to the participant directly. The participant may then perform the measurements themselves then return the form to staff via a prepaid envelope, email or via MyChart.
- Optional correlative blood samples collection (2 months follow-up only). Additional blood samples may be drawn at this time point, if needed. The blood sample may be collected up to 3 weeks before or after the visit if the patient is having their blood drawn as standard of care in order to prevent additional blood draws. A blood questionnaire will be completed during the process of the blood draw, either before or after, to assist the study team with evaluation of the sample quality. Study staff may call the participant remotely to perform the blood questionnaire. If a participant declines the blood draw, the blood questionnaire will not be completed.
- Optional saliva samples (6 months follow-up only). A saliva questionnaire will be completed during the process of collecting the saliva, either before or after, to assist the study team with evaluation of the sample quality. Study staff may call the participant remotely to administer the saliva questionnaire. The blood and saliva will

not be collected if the Biospecimen and Molecular Pathology Shared Resource at the Huntsman Cancer Institute is closed at the time of collection. Saliva samples will not be completed during the COVID-19 outbreak to ensure study personnel safety. The collection of saliva samples may resume if the study team decides the risk to study personnel safety is minimized.

Patients randomized to Group 1 will also receive in person, mail, via email, text, or MyChart the following:

- Review of tracking diary/calendar. It will not be a deviation if a participant does not return their diary as long as staff attempts to remind the participant to return it or if the participant declines to do it..
- If needed, adjustments to the mode/dose of the exercise regimen.
- A thank you letter only at the 6 month visit.

Patients randomized to group 2 will receive in person, mail, via email, text, or MyChart the following at the 6 month visit:

- A thank you letter
- The activity tracker with information relating to the tracker.
- Staff will offer the option to receive personalized exercises, but the participant may decline.

Staff may forego any of the above procedures if clinic policy does not allow (e.g. illness, virus outbreak, etc.).

If patients request to receive study materials and measurement results, the following may be given, mailed, emailed, texted, or sent via MyChart:

Copy of exercise diary, 6MW, or body measurements.

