3 STUDY DESIGN

3.1 Description

This is a Phase 3 study aimed at investigating the effects of a personalized exercise program (PEP) in NSCLC patients (stage I, II, IIIa) and secondary lung cancer patients undergoing surgical treatment at the University of Utah and comparing the intervention to the current standard of care (no exercise program).

Eligible patients will be randomized between two arms (1:1 ratio) prior to the surgery and will be followed for approximately 6 months post-surgery:

- An Intervention Arm (referred to in materials as Group 1), which features pre- and post-surgery PEP interventions.
- A Control Arm (referred to in materials as Group 2), which does not include a personalized exercise program (the standard of care). Patients randomized to Group

2 will be given the opportunity to participate in a PEP-intervention session providing exercise counseling after the 6 month assessment and will receive a free activity tracker for their participation.

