5 INTERVENTION

5.1 Group 2 Delayed Intervention Group

Patients randomized to Group 2 will not experience any changes in the standard of care for lung cancer patients according to their cancer stage. Although patients are encouraged to increase walking both in the pre-surgery and post-surgery period, there is no formalized pre-surgery exercise program. Upon study completion (at the 6 month post-surgery follow-up visit), participants in Group 2 will be offered a PEP-intervention session with precision exercise counseling and receive a free activity tracker.

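### The 6-month questionnaire stays open for a year after the visit at which Group 2 is given the tracker and offered PEP counselling, and no rule orders the two or handles late forms

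*Combined protocol and SAP*

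**What the plan says.** **Form window.** Section 8.7: "The 6 month questionnaire may be completed on the date of the visit up to one year after the visit". The same section lets patients take questionnaires home and return them in the weeks after the visit. It also lets staff mail them beforehand or hand them over at the visit.

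**Group 2 handover.** Section 5.1: "Upon study completion (at the 6 month post-surgery follow-up visit), participants in Group 2 will be offered a PEP-intervention session", together with the free tracker. Section 8.7 repeats this as a visit procedure: "Patients randomized to group 2 will receive in person, mail, via email, text, or MyChart the following at the 6 month visit", and the list includes "The activity tracker with information relating to the tracker" and an offer of personalized exercises that the patient may decline. Section 3.1 places the session "after the 6 month assessment and will receive a free activity tracker for their participation".

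**Visit window.** In periods of unforeseen outside disruption, "the 6 month visit may be completed up to one year post-discharge", and that limit can be extended.

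**Contrast.** PROMIS is limited to 3 weeks either side of each follow-up visit (Section 8.7).

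**Use of the data.** Section 1.2 makes the questionnaire results Secondary Endpoint #2, and Section 9.2 compares them between arms. Section 10 says nothing about when a 6-month form must have been completed to count.

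**The concern.** The window for the 6-month form opens on the day controls gain access to part of the intervention, and it stays open for 12 months. Sections 5.2.2 and 2.6 treat the tracker as an active component, a motivational and self-monitoring aid. The form measures things PEP is meant to change: exercise motivation (BREQ-3), self-efficacy, quality of life (FACT-L), fatigue (FACIT-F) and sleep (PSQI). A control patient who answers after the session and tracker is still analysed as an unexposed control at 6 months.

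Timing is a second problem, and it applies to both arms. Several instruments have short recall: Section 7.1 gives 24 hours for the mDES and one week for the WHI emotion items. A late form therefore describes the patient on the later date, not at month 6. For Group 1, whose programme runs for about 6 months after surgery (synopsis), a late form may describe the period after PEP has ended.

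At stake is how the 6-month between-arm comparison of patient-reported outcomes can be interpreted. A form returned 11 months after the visit is within window, so nothing in the plan would flag it.

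**Working it through.** **Step 1. Order of events.**

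| Event | Timing | Section |
|---|---|---|
| Group 2 session offered | at the 6-month visit, on study completion | 5.1 |
| Group 2 session offered | after the 6-month assessment | 3.1 |
| Group 2 tracker and exercise offer | at the 6-month visit | 8.7 |
| 6-month questionnaire | visit date to visit date + 1 year | 8.7 |

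The wording in 3.1 and 5.1 implies assessment first. No section says that the assessment includes return of the form, or that the handover waits for it. The form window begins on the handover day and lies wholly on or after it.

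**Step 2. Latest date.** With the visit at its nominal time: 6 + 12 = 18 months after surgery. With the disruption window: 12 + 12 = 24 months after discharge, or later if that window is extended.

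**Step 3. Outcomes affected.**
- Affected: the 6-month questionnaire instruments listed in Section 7.
- Not affected: the primary endpoint (6MW at 2 months, Section 10.3). At 6 months, 6MW and SPPB are visit procedures, and the 7-day recall may be done up to 2 weeks before the visit.
- Affected only slightly: PROMIS, which can follow the handover by at most 3 weeks.

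**Step 4. Possible size.** Let f be the share of controls who answer after exposure and g the fraction of the PEP effect they have gained by then. The expected difference shrinks by the factor (1 − f·g). The documents give neither f nor g.

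The only power figure for a questionnaire outcome is 96% for 10 FACT-L points (Section 10.4). It cannot be reproduced, because no SD, correlation or time point is stated. Solving backwards with two-sided 0.05 (stated for the primary endpoint, assumed here), it implies a residual SD of about 16.5 at 75 per arm or 19.1 at 100 per arm. The dilution result is the same for either:

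- Non-centrality at 96%: 1.960 + 1.751 = 3.711
- Power after dilution: Φ(3.711 × (1 − f·g) − 1.960)

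| f·g | Example (assumed) | Difference | Calculation | Power |
|---|---|---|---|---|
| 0 | no exposed controls | 10 | Φ(1.751) | 96% |
| 0.025 | 5% of controls, half the effect | 9.75 | Φ(3.618 − 1.960) | 95% |
| 0.10 | 20% of controls, half the effect | 9.0 | Φ(3.340 − 1.960) | 92% |
| 0.20 | 20% of controls, full effect | 8.0 | Φ(2.969 − 1.960) | 84% |

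The table is illustrative: it assumes that the 96% applies at 6 months.

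**The case against.** The strongest reply is that the intended order is already there. Section 3.1 puts the session after the 6-month assessment, Section 5.1 puts it on study completion, and the offer is small. This stands in part. The plan does contain a sequence. What it lacks is a link between that sequence and the form, whose window runs for a further year.

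A reader might infer that controls cross over to PEP. The documents do not support that. Group 2 is offered one session, which may be declined, plus a tracker. Group 1 has exercise before surgery, inpatient sessions, weekly calls and repeated adjustment of the prescription. The perioperative part cannot be given at 6 months, and no weekly follow-up of Group 2 is described. A control gaining the full effect is therefore an extreme case.

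A reader might also infer that 6-month forms will commonly date from two years after surgery. The 24-month figure adds the full form window to a visit window that applies only during outside disruption. It is a limit, not an expectation.

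Nor does the discharge form share this fault. "The discharge questionnaire may be completed on the date of the visit up to the 2 month visit", so two time points could fall close together, but no handover to Group 2 happens there and the form does close.

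**Conclusion.** The overlap is certain from the text. Its frequency and effect are not. As written, the plan permits control questionnaires labelled 6-month to be completed after exposure to part of PEP, and permits answers in either arm to be up to a year apart. A smaller between-arm difference is the likely result. It is not assured, because late forms also mix stages of recovery in both arms and the net effect of that is unknown.

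The power loss should be read as a range, about 95% to 84% for f·g between 0.025 and 0.20, with the upper end of f·g extreme. A reader might take the fall from 96% to 84% as a finding. It is not one: f and g are both assumed, and the plan does not tie the 96% to any time point.

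The point is confined to questionnaire-based 6-month secondary and exploratory outcomes. It does not touch the primary analysis. It should be corrected because the remedy is cheap and these outcomes are compared between arms.

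**What to change.** 1. Reconcile Sections 3.1, 5.1 and 8.7 so that the Group 2 tracker and session are provided only once the 6-month questionnaire has been collected, or a fixed closing date has passed. Sending the form before the visit or completing it there is already allowed.
2. Replace the one-year window with one closing date that is the same in both arms, for example 4 weeks after the visit. A cut-off tied to the Group 2 handover would not do: Group 1 has no such date, and if the handover stayed at the visit the rule would discard ordinary take-home control forms.
3. Record the completion date of every form.
4. In Section 10, treat forms completed after the closing date as missing in both arms and handle them by multiple imputation. Section 10.3 names the method under the primary endpoint, so state that it also covers these outcomes.
5. Add a sensitivity analysis that includes the late forms.

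**Cost.** Changes of wording, a date field and one extra analysis. Some late forms leave the main analysis; how many cannot be judged from the documents. Some controls receive the tracker a few weeks later.
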